Grade 3 fever will be defined as temperature > 39.0°C (regardless the route used).

The investigator will assess the maximum intensity that occurred over the duration of the event for all unsolicited AEs (including SAEs) recorded during the study. The assessment will be based on the investigator's clinical judgement.

The intensity should be assigned to one of the following categories:

1 (mild)	=	An AE which is easily tolerated by the subject, causing minimal discomfort and not interfering with everyday activities.
2 (moderate)	=	An AE which is sufficiently discomforting to interfere with normal everyday activities.
3 (severe)	=	An AE which prevents normal, everyday activities

An AE that is assessed as Grade 3 (severe) should not be confused with a SAE. Grade 3 is a category used for rating the intensity of an event; and both AEs and SAEs can be assessed as Grade 3. An event is defined as 'serious' when it meets one of the pre-defined outcomes as described in Section 8.1.2.

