10.8.2. Re-vaccination phase

Analyses post the re-vaccination phase will be performed on the Total vaccinated cohort.

All safety analyses might be performed by age stratum (60-69 and \geq 70 YOA at the time of initial vaccination as in ZOSTER-003 study) when the size of the category is considered meaningful.

- The percentage of subjects with at least one local solicited AE, with at least one general solicited AE and with any solicited AEs during the solicited 7-day follow-up period will be tabulated with exact 95% CI after each vaccine dose and overall. The same tabulation will be performed for grade 3;
- The percentage of subjects reporting each individual solicited local and general AE during the solicited 7-day follow-up period will be tabulated with exact 95% CI. For all solicited symptoms, the same tabulation will be performed for grade 3 solicited AEs and for solicited general AEs with relationship to vaccination ;
- The percentage of subjects reporting temperature by half degree ($^{\circ}$ C) cumulative increments. Similar tabulations will be performed for any fever with a causal relationship to vaccination and for any fever resulting in a medically attended visit ;
- The proportion of subjects with at least one report of unsolicited AE classified by the MedDRA Preferred Terms and reported up to 30 days after each vaccination will be tabulated with exact 95% CI;
- The same tabulation will be performed for grade 3 unsolicited AEs and for unsolicited AEs with a relationship to vaccination. The proportion of AEs resulting in a medically attended visit will also be tabulated ;
- Total number/percentages of doses (per dose and overall) followed by AEs will be tabulated;
- Number of subjects with pIMDs will be tabulated;
- All SAEs will be tabulated;
- SAEs related to vaccine will be tabulated and described;
- SAEs related to study participation or to GSK concomitant medication/vaccine will be tabulated and described;
- Adverse events (AEs)/SAEs leading to withdrawal from the study will be tabulated;
- Intercurrent medical conditions will be tabulated.

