6.3.2. Re-vaccination phase

The primary analysis for safety will be based on the TVC for re-vaccination course.

Safety and reactogenicity analyses will be performed overall and by age category at dose 1 of initial vaccination in ZOSTER-003 [60-69, ≥ 70 YOA] if the number of subjects is sufficient in each stratum.

When appropriate, tabulations will be presented overall and by time of occurrence relative to last vaccination (e.g., using windows such as Days 0-6, Days 0-29 and more than 30 days post-vaccination).

The results for the analysis of safety will be tabulated as follows:

- The number and percentage of subjects with at least one local solicited AE, with at least one general solicited AE and with any solicited AE during the 7-day follow-up period with exact 95% CIs after each vaccine dose and overall will be provided; the same tabulation will be performed for grade 3 symptoms and for solicited and unsolicited symptoms.
- The percentage of subjects reporting each individual solicited local and general AE during the solicited 7-day follow-up period will be tabulated with exact 95% CI;
- For all solicited symptoms, the same tabulation will be performed for grade 3 solicited AEs and for solicited general AEs with relationship to vaccination;
- Summary of temperature value by half degree increment reported during the 7-day (Days 0-6) post-vaccination period following each dose and subjects
- Number of days with solicited symptoms will be tabulated
- The proportion of subjects/doses with at least one report of unsolicited AE classified by the MedDRA preferred terms and reported up to 30 days after each vaccination will be tabulated with exact 95% CI;
- The same tabulations will be performed for grade 3 unsolicited AEs (not including SAEs) and for unsolicited AEs with a relationship to vaccination. The proportion of AEs resulting in a medically attended visit will also be tabulated;
- Number and percentage of subjects with pIMDs classified by the MedDRA preferred terms will be tabulated and described in detail; the same for SAEs.
- SAEs and withdrawal due to AE(s) will be described in detail.
- Potential and confirmed HZ cases identified during the study will be listed.

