7.2.2.5. Unsolicited symptoms

All vaccinated subjects will be considered for the analysis of unsolicited symptoms.

The analysis of unsolicited adverse events, including SAEs, consists of evaluating the percentage of subjects with at least 1 report of an unsolicited adverse event classified by MedDRA.

Subjects who missed reporting unsolicited symptoms will be treated as subjects without unsolicited symptoms.

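### SAP 6.3.2 leaves SAEs out of the grade 3 unsolicited AE table, against the protocol and undeclared, so that percentage can fall below the protocol's version

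*SAP*

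**What the plan says.** Four texts bear on one table, the percentage of subjects with a grade 3 unsolicited AE within 30 days of a dose.

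- **SAP Amendment 1, 6.3.2:** "The same tabulations will be performed for grade 3 unsolicited AEs (not including SAEs". The exclusion is attached to the grade 3 tabulation only.
- **Protocol 10.8.2:** "The same tabulation will be performed for grade 3 unsolicited AEs and for unsolicited AEs with a relationship to vaccination". No exclusion.
- **Protocol 8.2.3.2.1:** the investigator assesses maximum intensity "for all unsolicited AEs (including SAEs) recorded during the study", and the section adds that "both AEs and SAEs can be assessed as Grade 3".
- **SAP Amendment 1, 7.2.2.5:** "The analysis of unsolicited adverse events, including SAEs, consists of evaluating the percentage of subjects with at least 1 report" of an unsolicited event.

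SAEs also have their own output. SAP 6.3.2 says that subjects with pIMDs, counted by preferred term, "will be tabulated and described in detail; the same for SAEs". No split by intensity is mentioned.

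SAP version 1, section 6.3, carried the grade 3 tabulation with no exclusion, so the exclusion entered with Amendment 1. The document history describes that amendment as a closer match to the protocol and to the approved tables, with no major change. Section 9, on changes from planned analyses, records NA.

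**The concern.** The SAP gives two rules for one table, and the more specific rule departs from the protocol. A subject whose only severe event was serious is counted among subjects with any unsolicited AE but not among those with a grade 3 event. Occurrence, intensity and relationship of unsolicited AEs over Days 0-29 is a listed secondary endpoint in both documents, and the grade 3 row is its main intensity summary. In one uncontrolled group of about 100 subjects, one or two people can visibly move that row. A reader who relies on SAP 7.2.2.5 would assume that SAEs are in it.

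**Working it through.** **1. Which events does the protocol's table contain?** Protocol 8.1.1 treats every AE that is not solicited as unsolicited. Section 8.2.3.2.1 counts SAEs among unsolicited AEs and has them graded. Section 10.8.2 tabulates grade 3 unsolicited AEs without restriction. Read together, grade 3 SAEs within the 30-day window belong in the table. Section 10.8.2 does not say so itself; the reading rests on the other two sections. The change list of Protocol Amendment 1 shows no edit to 8.2.3.2.1 or 10.8.2, so the protocol amendment does not explain the difference. SAP 7.2.2.5 agrees with the protocol, and SAP 6.3.2 is narrower than both.

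**2. Size of the difference.** The documents give no expected grade 3 or SAE rate, so there is no figure of the plan's to reproduce. Let

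- N = vaccinated subjects (about 100 planned, protocol section 3, Table 1; 60 is my assumption to show attrition),
- x = subjects with at least one non-serious grade 3 unsolicited AE in the window,
- k = subjects whose only grade 3 unsolicited event in the window is an SAE.

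SAP version = x/N. Protocol version = (x + k)/N. Shortfall = k/N, which cannot be negative.

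Per affected subject this is 1/100 = 1.0 percentage point, or 1/60 = 1.7. With x = 3 assumed, and the exact Clopper-Pearson 95% intervals that SAP 7.4.1 specifies:

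| k | N = 100 | N = 60 |
|---|---|---|
| 0 (also the SAP version for every k) | 3.0% (0.6 to 8.5) | 5.0% (1.0 to 13.9) |
| 1 | 4.0% (1.1 to 9.9) | 6.7% (1.8 to 16.2) |
| 2 | 5.0% (1.6 to 11.3) | 8.3% (2.8 to 18.4) |
| 3 | 6.0% (2.2 to 12.6) | 10.0% (3.8 to 20.5) |

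**3. How likely is any difference?** If each subject has probability p of being such a case, the chance that k is at least 1 is 1 - (1 - p)^N. The values of p are assumptions.

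| p | N = 100 | N = 60 |
|---|---|---|
| 0.2% | 18% | 11% |
| 0.5% | 39% | 26% |
| 1% | 63% | 45% |
| 2% | 87% | 70% |
| 3% | 95% | 84% |

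**4. Can the SAE table fill the gap?** Not as described. Some SAEs may not be grade 3, and a subject may also have a non-serious grade 3 event and so appear in both tables. Suppose N = 100, x = 3, and 3 subjects have an SAE in the window. The protocol's percentage could then be anything from 3/100 = 3.0% (no SAE adds a new grade 3 subject) to (3 + 3)/100 = 6.0% (all three do). Adding the two tables does not settle it.

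**The case against.** The case for leaving the text alone has several sound parts.

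- *SAEs are not lost.* They are counted by preferred term and described in detail, and no exclusion is stated for the all-grade or vaccine-related unsolicited tables. In a group this small, a grade 3 SAE could be identified individually, since its intensity is collected. This stands.
- *Timing is provided for.* SAP 6.3.2 allows tabulations by window, Days 0-29 among them, when appropriate. An SAE table for that window is possible, though not assured. What remains missing is the split by intensity.
- *Another grade 3 summary exists.* The first bullet of SAP 6.3.2 mentions grade 3 and unsolicited symptoms with no SAE exclusion. Its wording is ambiguous and it extends a 7-day summary, so it does not clearly replace the 30-day preferred-term table.
- *The specific rule governs.* SAP 7.2.2.5 is a general statement under missing-data handling, and 6.3.2 can be read as an explicit exception. That would tell the programmer what to do, but it confirms the departure from the protocol.
- *The change may be covered elsewhere.* The table annex is not available here, and protocol 10.10 requires changes to be described and justified in the final report. So the lack of a declaration is a statement about the SAP only.
- *Nothing is tested.* All analyses are descriptive, and no decision rule uses this row. This limits the consequence.

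A reader might also infer that the grade 3 row is no longer a subset of the any-event row. It still is: every subject with a non-serious grade 3 unsolicited AE has an unsolicited AE, and both rows use all vaccinated subjects as denominator. Nor do the documents support an argument that severe events in this age group are mostly hospitalisations; they give no such data.

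**Conclusion.** The discrepancy is real. SAP 6.3.2 is narrower than protocol 10.8.2 read with 8.2.3.2.1, conflicts with SAP 7.2.2.5, and is not recorded in SAP section 9. Its effect is confined to one descriptive table and runs in one direction.

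A reader might conclude that the severe-event rate after re-vaccination is understated. The documents support only that it can be. There is no effect unless at least one subject has a grade 3 SAE within 30 days of a dose and no other grade 3 unsolicited AE in that window. The k/N formula needs no assumed event rate; the illustrative percentages and probabilities do. The point is worth correcting because the row summarises a named secondary endpoint and no other output is stated to give the same number.

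**What to change.** In SAP 6.3.2, delete the parenthetical exclusion of SAEs so that the grade 3 unsolicited table covers serious and non-serious events, as in the protocol. A row restricted to non-serious events may sit beneath it.

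If the sponsor prefers to keep the exclusion, present the grade 3 table both with and without SAEs, amend SAP 7.2.2.5 to agree, and record the change with its reason in SAP section 9.

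The cost is three words deleted and one table rerun. Protocol 8.2.3.2.1 already requires an intensity grade for SAEs, so no new data are needed.

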7. STATISTICAL CALCULATIONS

7.1. Derived and transformed data

7.1.1. Demography

For a given subject and a given demographic variable, missing measurement will not be replaced except for age.

7.1.1.1. Age at vaccination

Age will be calculated as the number of years between the date of birth and the date of first vaccination (either at first initial vaccination dose or at the first re-vaccination dose as specified).

To ensure that the collection of date of birth will not jeopardize the privacy of Personally Identifiable Information (PII), only a partial date of birth (MMYYYY) will be collected.

Therefore, the 15th of the month will be used to replace the missing date.

In case the month is missing, the date will be replaced by the June 30th of the year.

7.1.2. Immunogenicity

7.1.2.1. CMI response

- The log-transformation of the frequency of CD4+T-cells producing at least 2 immunological activation markers (IFN- γ , IL-2, TNF- α and /or CD40L, termed “all doubles” or CD4[2+]) upon in vitro stimulation with the antigen (induction condition) is calculated by adding an offset of 0.5 to the number of activated CD4+T-cells producing at least 2 immunological activation markers (“all doubles”, CD4[2+]) upon in vitro stimulation in medium only (background condition).

$$Freq_{Induction}^{CD4\ 2+} = \frac{n_{Induction}^{2+} + 0.5}{N_{Induction}^{CD4}} \quad Log_e(Freq_{Induction}^{CD4\ 2+}) = Log_e\left(\frac{n_{Induction}^{2+} + 0.5}{N_{Induction}^{CD4}}\right)$$

$$Freq_{Background}^{CD4\ 2+} = \frac{n_{Background}^{2+} + 0.5}{N_{Background}^{CD4}} \quad Log_e(Freq_{Background}^{CD4\ 2+}) = Log_e\left(\frac{n_{Background}^{2+} + 0.5}{N_{Background}^{CD4}}\right)$$

$n_{Induction}^{2+} =$	Number of antigen – specific T-cells expressing at least 2 cytokines
$n_{Background}^{2+} =$	Number of CD4 T-cells expressing at least 2 cytokines in the medium only
$N^{CD4} =$	Total number of CD4 involved in the assay (induction or background)

- The individual frequency of antigen – specific (gE) CD4+T-cells is calculated as the difference between the frequency of CD4+T-cells producing at least 2 immunological activation markers (“all doubles”, CD4[2+]) upon in vitro stimulation

in medium only (background condition). When the log-transformation is applied to that variable prior to analysis, differences less or equal to zero (0) are imputed to 1 gE -specific cytokine secreting CD4+T-cells per 10^6 CD4+T-cells.

$$Freq_{Specific}^{CD4\ 2+} = \frac{n_{Induction}^{2+} + 0.5}{N_{Induction}^{CD4}} - \frac{n_{Background}^{2+} + 0.5}{N_{Background}^{CD4}}$$

$$\text{Log}_e(Freq_{Specific}^{CD4\ 2+}) = \text{Log}_e\left(\frac{n_{Induction}^{2+} + 0.5}{N_{Induction}^{CD4}} - \frac{n_{Background}^{2+} + 0.5}{N_{Background}^{CD4}}\right) \text{ if } \frac{n_{Induction}^{CD4\ 2+}}{N_{Induction}^{CD4}} > \frac{n_{Background}^{CD4\ 2+}}{N_{Background}^{CD4}}$$

$$\text{Log}_e(Freq_{Specific}^{CD4\ 2+}) = \text{Log}_e\left(\frac{1}{10^6 \text{ cells}}\right) \text{ if } \frac{n_{Induction}^{CD4\ 2+}}{N_{Induction}^{CD4}} \leq \frac{n_{Background}^{CD4\ 2+}}{N_{Background}^{CD4}}$$

- The Geometric Mean (GM) calculations are performed by taking the anti-log of the mean of the log frequency transformations.
- The vaccine response after vaccination or after re-vaccination for the frequency of gE-specific CD4(2+) T-cells over pre-vaccination in the initial ZOSTER-003 study is defined as follows:
 - For initially subjects with pre-vaccination T cell frequencies below the threshold, at least a 2-fold increase as compared to the threshold (2x<320> Events/10E6 CD4+ T cells)
 - For initially subjects with pre-vaccination T cell frequencies above the threshold, at least a 2-fold increase as compared to pre-vaccination T cell frequencies

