10.5.3. CMI response

For the descriptive analyses, the frequency of CD4[2+] T-cells upon in vitro stimulation with the gE-antigen (induction condition) is calculated by dividing the number of activated CD4[2+] T-cells (numerator) over the total number of CD4 T-cells involved (denominator). The same calculation will be performed for the frequency computation for any kinds of cells and for each individual activation marker as appropriate.

$$Freq_{CD4[2+]} = \frac{n_{Induction}^{2+}}{N_{CD4}}$$

$n_{Induction}^{2+}$ = number of CD4 T – cells secreting at least 2 activation markers after induction with the antigen

N_{CD4} = Total number of CD4 T – cells involved in the assay (induction)

The frequency of gE-specific CD4 T-cells for each individual subject is calculated as the difference between the frequency of CD4[2+] T-cells, upon in vitro stimulation with the gE antigen (induction condition) minus the frequency of CD4[2+] T-cells upon in vitro stimulation in medium only (background condition). The differences less or equal to one are imputed to one gE-specific CD4[2+] T-cell per 10^6 CD4+ T-cells. The same calculation will be performed for the frequency computation for any kind of cells and for each individual activation marker as appropriate.

$$Freq_{Specific}^{CD4[2+]} = \frac{n_{Induction}^{2+}}{N_{Induction}^{CD4}} - \frac{n_{Background}^{2+}}{N_{Background}^{CD4}}$$

$$if \frac{n_{Induction}^{2+}}{N_{Induction}^{CD4}} > 1 + \frac{n_{Background}^{2+}}{N_{Background}^{CD4}}$$

$$Freq_{Specific}^{CD4[2+]} = 1$$

$$if \frac{n_{Induction}^{2+}}{N_{Induction}^{CD4}} \leq 1 + \frac{n_{Background}^{2+}}{N_{Background}^{CD4}}$$

$n_{Induction}^{2+}$ = number of CD4 T - cellssecreting at least 2 activation markers after induction with the gE - antigen

$n_{Background}^{2+}$ = number of CD4 T - cellssecreting at least 2 activation markers in the medium conditions

N^{CD4} = Total number of CD4 T - cellsinvolved in the assay (induction of background)

- The GM frequency calculations are performed by taking the anti-log of the mean of the log frequency transformations.
- The CMI vaccine response to gE will be based on the gE-specific data as computed above. The lower limit of linearity (LLL) for the assay will be used as threshold for vaccine response assessment and the estimated value will be detailed in the Statistical Analysis Plan (SAP). The Vaccine Response (VR) is defined as the percentage of subjects who have:

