10.7.2. Assessment of re-vaccination phase

The analysis of re-vaccination phase will be based on the ATP cohort for analysis of immunogenicity. If, the percentage of vaccinated subjects with serological results excluded from the ATP cohort for analysis of immunogenicity is 5% or more, a second analysis based on the TVc will be performed to complement the ATP analysis.

All analyses will be performed overall and by age stratum (60-69, ≥ 70 YOA at time of initial vaccination in study ZOSTER-003) if the number of subjects is sufficient in each stratum.

Humoral Immune response endpoint

For the humoral immune response, at each timepoint that a blood sample is available (at Months 120, 121 and 123) post-revaccination, the following parameters (with 95% CIs) will be tabulated overall, and by age group (60-69, ≥ 70 YOA at time of initial vaccination in study ZOSTER-003):

- Geometric mean concentrations (GMCS) of anti-gE Ab with 95% confidence interval (CIs);
- Humoral seropositivity rates with exact 95% confidence interval (CIs);
- Vaccine response rates [post re-vaccination over pre-vaccination in the initial study] with 95% confidence interval (CIs);

- The geometric mean of the ratio Post Month 1 (Month 121) and post Month 3 (Month 123) post re-vaccination (current study) over Visit Month 0 (Month 120), in the current study with 95% CI;
- The geometric mean of the ratio Post Month 1 (Month 121) and post Month 3 (Month 123) post re-vaccination (current study) over pre-vaccination in the initial study with 95% CI;
- The distribution of antibody titres will be tabulated and also presented using reverse cumulative curves.

CMI endpoint

For CMI response, the following parameters (for gE specific CD4[2+] frequency and CD4[+2] T-cell following induction with gE) will be tabulated overall and by age group (60-69, ≥ 70 YOA at time of initial vaccination in study ZOSTER-003) at Months M0 (Month 120), M1 (Month 121) and M3 (Month 123) post re-vaccination:

Descriptive statistics (N, mean, SD, min, Q1, median, Q3, max) of the following parameters will be tabulated:

- Descriptive statistics of the frequency of CD4+ T-cells secreting at least two activation markers (from among IFN- γ , IL-2, TNF- α , CD40L) for gE-specific stimulation.

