- Descriptive statistics (N, mean, SD, min, Q1, median, Q3, max) for the following parameters will be tabulated at Months 0, 3, 12, 24, 36, 48, 60, 72, 108 and 120 post first dose of initial vaccination overall and some by age category at dose 1 of initial vaccination in ZOSTER-003 [60-69, ≥ 70 YOA]:
 - the frequency of gE specific CD4+T-cells secreting at least 2 activation markers (among IFN- γ , IL-2, TNF- α , CD40L)
 - the frequency of CD4+T-cells following induction with gE secreting at least two activation markers (among IFN- γ , IL-2, TNF- α , CD40L)
 - the fold increase over pre-vaccination in the frequency of gE-specific CD4(2+) T-cells
 - the fold increase over pre-vaccination in the frequency of CD4(2+) T-cells following induction with gE
- Vaccine response rates of frequency of gE-specific CD4(2+) T-cells up to Month 120 post-vaccination will be tabulated with 95% CI

Exploratory analysis

- A piece-wise linear mixed model, power law model and modified power law model [David, 2009] for repeated measurements (all data available from month 0, 3, 12, 24, 36, 48, 60, 72, 108 and 120 post first dose of initial vaccination) will be used to model over time
 - the frequency of gE specific CD4+T-cells secreting at least 2 activation markers (among IFN- γ , IL-2, TNF- α , CD40L)
 - the frequency of CD4+T-cells following induction with gE secreting at least 2 activation markers (among IFN- γ , IL-2, TNF- α , CD40L)
 - the gE antibody concentrations
- The three models based on data up to M120 will be presented graphically. Models based on data up to M108 and on data up to M120 will be presented side by side.

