6.2.2. Assessment of re-vaccination phase

The analysis of re-vaccination phase will be based on the ATP cohort for analysis of immunogenicity after re-vaccination. If, the percentage of vaccinated subjects with serological results excluded from the ATP cohort for analysis of immunogenicity after re-vaccination is 5% or more, a second analysis based on the TVC will be performed to complement the ATP analysis.

All analyses will be performed overall and by age category at dose 1 of initial vaccination in ZOSTER-003 (60-69, ≥ 70 YOA) if the number of subjects is sufficient in each stratum.

Humoral Immune response

- At each timepoint that a blood sample is available (at Months 120, 121 and 123) post-re-vaccination, the following parameters will be tabulated overall and some by age category at dose 1 of initial vaccination in ZOSTER-003 (60-69, ≥ 70 YOA):
 - GMCs of anti-gE Ab with 95% confidence interval (CIs);
 - Anti-gE seropositivity rates with exact 95% confidence interval (CIs);
 - Vaccine response rates [post re-vaccination (M121 and M123) over pre-vaccination in the initial ZOSTER-003 study] with 95% confidence interval (CIs);
 - MGI (geometric mean of the ratio) Post Month 1 (Month 121) and post Month 3 (Month 123) post re-vaccination (current study) over Pre-re-vaccination (Month 120), with 95% CI;
 - Descriptive statistics of the fold increase over pre-re-vaccination at months 121 and 123 (mean, standard deviation, min, Q1, median, Q3, max).
 - Distribution of the fold increase over pre-re-vaccination at months 121 and 123
 - MGI (geometric mean of the ratio) Post Month 1 (Month 121) and post Month 3 (Month 123) post re-vaccination (current study) over pre-vaccination in the initial ZOSTER-003 study, with 95% CI;
- The distribution of antibody titers at Months 120, 121 and 123 will be presented using reverse cumulative curves.

CMI response

- Descriptive statistics (N, mean, SD, min, Q1, median, Q3, max) for the following parameters will be tabulated at Months 120, 121 and 123 overall and some by age category at dose 1 of initial vaccination in ZOSTER-003 [60-69, \geq 70 YOA]:
 - the frequency of gE specific CD4+T-cells secreting at least 2 activation markers (among IFN- γ , IL-2, TNF- α , CD40L)
 - the frequency of CD4+ T-cells following induction with gE secreting at least 2 activation markers (among IFN- γ , IL-2, TNF- α , CD40L)
 - the fold increase over pre-re-vaccination in the frequency of gE specific CD4[2+] T-cells at months 121 and 123

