6.2.3. Assessment of persistence after re-vaccination

Persistence data will be analyzed at Month 134 timepoint after re-vaccination (i.e. 12 months after last dose of re-vaccination).

The analysis of antibody persistence after re-vaccination at Month 134 will be based on the ATP cohort for analysis of immunogenicity at Y11. If the percentage of subjects who come back for this follow-up with serological results excluded from the ATP cohort is higher than 5%, a second analysis based on the TVC for revaccination course will be performed to complement the ATP analysis.

Humoral immune response:

- If a blood sample is available at Month 120, 121, 123 and 134, the following parameters (with 95% CIs) will be tabulated overall and some by age group (60-69, ≥ 70 YOA at time of initial vaccination in study ZOSTER-003):
 - GMCs of anti-gE Ab with 95% confidence interval (CIs);
 - Anti-gE seropositivity rates with exact 95% confidence interval (CIs);
 - Vaccine response rates [post re-vaccination over pre-vaccination in the initial ZOSTER-003 study] with 95% confidence interval (CIs);
 - MGI (geometric mean of the ratio) post re-vaccination (current study) over Pre-re-vaccination (Month 120), with 95% CI;
 - Descriptive statistics of the fold increase over pre-re-vaccination at months 121, 123 and 134 (mean, standard deviation, min, Q1, median, Q3, max).
 - Distribution of the fold increase over pre-re-vaccination at months 121, 123 and 134
 - MGI (geometric mean of the ratio) post re-vaccination (current study) over pre-vaccination in the initial ZOSTER-003 study, with 95% CI;
- The distribution of antibody titers at Months 121, 123 and 134 will be presented using reverse cumulative curves.

CMI response:

- Descriptive statistics (N, mean, SD, min, Q1, median, Q3, max) for the following parameters will be tabulated at Months 120, 121, 123 and 134 overall and some by age category at dose 1 of initial vaccination in ZOSTER-003 [60-69, ≥ 70 YOA]:
 - the frequency of gE specific CD4+T-cells secreting at least 2 activation markers (among IFN- γ , IL-2, TNF- α , CD40L)
 - the frequency of CD4+ T-cells following induction with gE secreting at least 2 activation markers (among IFN- γ , IL-2, TNF- α , CD40L)
 - the fold increase over pre-re-vaccination in the frequency of gE specific CD4[2+] T-cells at months 121, 123 and 134
 - the fold increase over pre-re-vaccination in the frequency of CD4[2+] T-cells following induction with gE at months 121, 123 and 134

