 - the fold increase over pre-vaccination in the initial ZOSTER-003 study in the frequency of gE specific CD4[2+] T-cells at months 121, 123 and 134
 - the fold increase over pre-vaccination in the initial ZOSTER-003 study in the frequency of CD4[2+] T-cells following induction with gE at months 121, 123 and 134
- Vaccine response rates of frequency of gE-specific CD4(2+) T-cells at Months 121, 123 and 134 over pre-vaccination in the initial ZOSTER-003 study will be tabulated with 95% CI.

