9. CHANGES FROM PLANNED ANALYSES

NA

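### Protocol and SAP derive the gE-specific CD4[2+] frequency differently, and the SAP gives no stated floor for the denominators of its un-logged fold tables

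*SAP*

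**What the plan says.** **Protocol 10.5.3** introduces its derivation as serving the descriptive analyses. The gE-specific frequency is n/N after induction minus n/N in medium, with no offset. The floor carries no condition about logs: "The differences less or equal to one are imputed to one gE-specific CD4[2+] T-cell per 10^6 CD4+ T-cells".

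**SAP 7.1.2.1** (Amendment 1) adds 0.5 to each count before dividing. Its floor starts at zero and is tied to logs: "When the log-transformation is applied to that variable prior to analysis, differences less or equal to zero (0) are imputed to 1" (per 10^6 CD4+ T-cells). The printed formulas agree with that sentence: the un-logged specific frequency has no floor, and only its logarithm has one.

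**Folds.** SAP 6.2.1 tabulates N, mean, SD, minimum, quartiles, median and maximum of "the fold increase over pre-vaccination in the frequency of gE-specific CD4(2+) T-cells". SAP 6.2.2 adds "the fold increase over pre-re-vaccination in the frequency of gE specific CD4[2+] T-cells at months 121 and 123". SAP 6.2.3 extends both kinds of fold to Month 134, including "the fold increase over pre-vaccination in the initial ZOSTER-003 study in the frequency of gE specific CD4[2+] T-cells at months 121, 123 and 134". None of these sections mentions a log or a rule for a zero or negative denominator. The protocol plans a CMI fold only over Month 0 in the persistence phase (10.7.1). For CMI after re-vaccination, 10.7.2 and 10.7.3 list frequencies only: "Descriptive statistics of the frequency of CD4+ T-cells secreting at least two activation markers".

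**Disclosure.** The entry under "9. CHANGES FROM PLANNED ANALYSES" in the SAP is NA.

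**The concern.** The two derivations differ in three ways: the offset (none against 0.5), the floor trigger (at or below 1 against at or below 0) and its scope (always against only when logged).

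Scope matters most. A background-subtracted frequency can be zero or negative, and a fold divides by it. If the un-logged SAP formula is followed, a subject who started with no measurable response and then responded strongly gets a negative fold and falls to the bottom of the ranking. Enough such subjects pull down the median and quartiles, not only the mean and minimum.

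The study is purely descriptive, so these tables are themselves results. Two programmers, one following each document, would produce different ones.

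**Working it through.** The plan states no figure on this point, so there is nothing to reproduce. The documents also give no background rate, cell totals or number of baselines at or below background. All counts below are assumptions.

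**1. The two rules on the same counts** (per 10^6; follow-up value 1000)

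- Protocol: d = 10^6 × (n_ind/N_ind − n_bg/N_bg), set to 1 if d ≤ 1.
- SAP un-logged: d = 10^6 × ((n_ind + 0.5)/N_ind − (n_bg + 0.5)/N_bg), no floor.

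| Baseline counts (induction; background) | Protocol d | Protocol fold | SAP un-logged d | SAP fold |
|---|---|---|---|---|
| 20/200,000; 30/200,000 | 1 (raw −50) | 1000 | −50 | −20 |
| 30/200,000; 30/200,000 | 1 (raw 0) | 1000 | 0 | undefined |
| 30/200,000; 29/200,000 | 5 | 200 | 5 | 200 |

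With equal totals the offset cancels, so only the floor separates the two rules.

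**2. Effect on the median fold.** Suppose a share p of baselines lies below background and the other folds are log-normal with median 10 and log SD s. For quantile q, let x be the matching quantile among the unaffected folds:

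- Literal SAP (affected folds rank lowest): x = (q − p)/(1 − p).
- Excluded as non-evaluable: x = q.
- Floored (affected folds rank highest): x = q/(1 − p).

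The value is 10 × exp(s × z_x). At p = 0.10, q = 0.5, s = 1.0, the literal x is 0.40/0.90 = 0.444, z = −0.140, value 8.70. The floored x is 0.50/0.90 = 0.556, value 11.50.

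| Affected per 100 | Literal (s = 0.7 to 1.3) | Excluded | Floored (s = 0.7 to 1.3) |
|---|---|---|---|
| 1 | 9.8–9.9 | 10 | 10.1–10.2 |
| 5 | 9.2–9.5 | 10 | 10.5–10.9 |
| 10 | 8.3–9.1 | 10 | 11.0–12.0 |

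The lower quartile at 10 per 100 is 2.8–5.1 literal, 4.2–6.2 excluded and 4.6–6.6 floored.

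**3. Effect on the mean.** Take nine subjects with fold 10 and one with baseline −50 and follow-up 1000. Literal: (90 − 20)/10 = 7. Excluded: 90/9 = 10. Floored: (90 + 1000)/10 = 109. The median is 10 in all three. The floor restores sign and rank but does not stabilise the arithmetic mean.

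**4. What does not move**

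- CMI response rate: a baseline below 320 per 10^6 is compared with 2 × 320 = 640, so a floor at 1 cannot matter.
- Induction-only folds: the denominator (n + 0.5)/N is always positive.
- Geometric means: they go through logs and keep a floor, apart from step 5.
- Primary frequency tables: if 5 of 100 values were −40 instead of 1, the mean would move by 5 × 41/100 = 2.05 per 10^6. The minimum could be negative.

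**5. Side point on the SAP's log condition.** The condition tests n/N, but the quantity logged is the difference of (n + 0.5)/N. The two differ by 0.5 × 10^6 × (1/N_ind − 1/N_bg), which is negative whenever the background total is the smaller.

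- 61/300,000 against 20/100,000: the raw difference is +3.33 and passes the test; the logged quantity is 205 − 205 = 0.
- 5/100,001 against 4/80,003: the raw difference is +0.0014 and passes; the logged quantity is −1.25.

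The second case shows that strongly unequal totals are not needed. A near-tie is enough.

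**The case against.** The best reply is that the two rules can stand together. Protocol 10.5.3 says it serves the descriptive analyses, and the folds are descriptive. The SAP floor then concerns only logged values. The SAP's document history says Amendment 1 was made to match the protocol better. A programmer could also use SAP 7.2.1, which excludes non-evaluable measurements, and drop any fold over a non-positive baseline. Under either reading no fold over such a baseline is negative.

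This stands as far as it goes: the literal reading is one of several. It does not remove the problem, because the readings give different tables and the SAP chooses none. The SAP prints its own un-logged formula without reference to 10.5.3. Section 7.2.1 does not clearly settle it either, since the baseline frequency is measured even when it is negative.

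The protocol rule is also not usable exactly as printed. Its condition compares n/N with 1 plus n/N, which proportions can never satisfy. It works only if the 1 is read as 1 per 10^6, as the accompanying sentence indicates.

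On disclosure, protocol 10.10 sends deviations to the final study report, so the NA in SAP section 9 is not the last opportunity to record the difference. The re-vaccination CMI folds that appear only in the SAP are extra descriptive tables, not an error.

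**Conclusion.** The inconsistency is certain; its effect is conditional and modest. The text supports a difference in offset, floor trigger and scope, with no entry in SAP section 9. Undefined or negative folds follow only if the un-logged SAP formula is programmed as printed and some baselines lie at or below background.

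The sizes rest on the assumed log-normal folds and on an unknown number of affected baselines: negligible at about 1 per 100, and a spread in the median from about 8–9 to 11–12 at 10 per 100. Folds over Month 0 are probably more exposed than folds over Month 120, because protocol 1.2.1 reports responses still above baseline at Month 72.

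A reader might infer that the primary persistence results or the CMI response rates are compromised, or that negative folds will certainly be reported. The documents support neither. The primary tables barely move, the response-rate rule bypasses low baselines, there is no hypothesis test, and other readings of the fold rule are open. The harm is confined to secondary descriptive fold tables. It is still worth correcting, because a printed rule can reverse a subject's rank.

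**What to change.** In SAP 7.1.2.1, state one derivation on the per-10^6 scale:

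- Frequency = 10^6 × n/N. A gE-specific difference of 1 or less is set to 1.
- Test the floor on the same quantity that is analysed. Apply it before any log, geometric mean or fold, in both numerator and denominator.
- Keep the 0.5 offset only for the logs of the induction and background frequencies. This also removes the log-condition mismatch.

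In protocol 10.5.3, correct or clarify the printed condition so that the 1 means 1 per 10^6. Record any remaining difference in SAP section 9. Report the number of floored baselines beside each gE-specific fold table, and lead with the planned median and quartiles.

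The cost is a short rewording of SAP 7.1.2.1, a scale clarification in the protocol, a line in SAP section 9 if any difference remains, one derivation line in the dataset program and one count per table. No new data are needed. The downside is that floored baselines give very large individual folds, so the arithmetic mean, SD and maximum stay unstable and should not be the headline.
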